8.3 Recording and Reporting

An emergency contact will be assigned to each participant in case of any unexpected circumstances. In occurrence of an AE, it will be graded according to the DAIDS severity grading system ICH 6:

- ⑩ Mild: participant was able to perform all normal activities
- ⑩ Moderate: the participant had to discontinue some activities due to the AE
- ⑩ Severe: the participant was incapacitated by the AE and unable to perform normal activities
- ⑩ Life-threatening: participant experienced extreme limitation in activity, significant assistance required; significant medical intervention/therapy required, hospitalization probable

Investigators will assess the occurrence of AEs and SAEs at all follow up time points during the study. All AE/SAE will be recorded and reported in detail, with further investigation into the relationship between each AE and the clinical procedures.

9. Record Form & Retention

All data related to this study in both paper and electronic form will be available only to the research team and the legal supervisors. The original data are the property of the investigation team and are inaccessible to any other third parties. The researchers from the team are ultimately responsible for the collection and analyze of the data. Any alterations to the original data must be documented. All the original data will be retained securely by the investigators both during and after the closure of the study in order to ensure evaluations or audits from regulatory authorities. If the investigator is unable to continue retaining the study records for the required period for any reason, the Emergency Response Group should be prospectively notified.

10. Ethics

The conduct of this study will abide by the laws and principles proclaimed in the Declaration of Helsinki. All managements and operations will be carried out under the supervision of The Institutional Review Board (IRB) & Hospital Ethics Committee (HEC).

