- ⑩ Adverse effects, including possible alteration of ocular structure and function, Cas9-specific immunoreaction or off-target editing of CRISPR in the bloodstream. Postoperative B-scan ultrasonography, time-domain OCT, spectral-domain OCT, and electroretinography (ERG) will be used to evaluate ocular status. ELISA and Whole-genome sequencing (WGS) will be conducted on the blood samples collected at 3-month and 6-month visit, respectively.

Table of Contents

1. Introduction	30
1.1 Study Objects.....	30
1.2 Backgrounds of HELP.....	30
2. Eligibility Criteria	30
2.1 Inclusion Criteria.....	30
2.2 Exclusion Criteria.....	31
3. Study Implementation	32
3.1 Study Design.....	32
3.2 Preparation of HELP Formulation.....	33
3.3 Corneal Transplant and HELP Administration.....	34
3.4 Post-operation Management.....	35
4. CRISPR/Cas9 Therapy Interruption	36
5. Quality Control	36
5.1 Quality Control and Quality Assurance.....	36
5.2 Monitoring.....	36
6. Data Collection and Evaluation	37
7. Statistical Considerations	38
8. Adverse Event Reporting	38
8.1 Adverse Event.....	38
8.2 Serious Adverse Event.....	38
8.3 Recording and Reporting.....	39
9. Record Form & Retention	40
10. Ethics	40

10.1	Ethical Conduct of the Study.....	40
10.2	Patient Information and Consent.....	40
11.	Reference.....	42

1. Introduction

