8.2 Serious Adverse Event Reporting

SAE is an AE with a potential outcome of death, prolonged hospitalization, disability or permanent damage, congenital anomaly/birth defect, or other serious important medical events. Specifically, SAE is any untoward medical occurrence that:

- ⑩ Results in death
- ⑩ Life-threatening
- ⑩ Requires extra hospitalization or prolongation of existing hospitalization
- ⑩ Results in persistent or significant disability/incapacity
- ⑩ Results in congenital anomaly/birth defect

All suspected SAEs related to the study should be followed up according to the institution's standard of care, preferably in consultation with leading specialists.

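### The severity grades in section 8.3 carry little information about harm to the treated eye, and the seriousness list in 8.2 is narrower than its own definition

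*Combined protocol and SAP*

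**What the plan says.** All references are to the current protocol (version 2.0) unless stated; sections 8.2 and 8.3 read the same in version 1.0.

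**Severity (8.3).** The rule is "In occurrence of an AE, it will be graded according to the DAIDS severity grading system ICH 6". No version of that system is cited and no eye-specific table is reproduced. Four anchors follow:
- "Mild: participant was able to perform all normal activities"
- "Moderate: the participant had to discontinue some activities due to the AE"
- "Severe: the participant was incapacitated by the AE and unable to perform normal activities"
- "Life-threatening: participant experienced extreme limitation in activity, significant assistance required; significant medical intervention/therapy required, hospitalization probable"

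There is no grade for death.

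**Seriousness (8.1 and 8.2).** Section 8.1 has the investigator check each event against the serious criteria, and a serious event must be notified immediately. The opening definition in 8.2 runs on to "disability or permanent damage, congenital anomaly/birth defect, or other serious important medical events". The itemised list beneath it has five entries: death, life-threatening, extra or prolonged hospitalisation, persistent or significant disability, and congenital anomaly.

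**What safety is meant to capture.** Under Outcomes Measures, the third secondary outcome is "Adverse effects, including possible alteration of ocular structure and function, Cas9-specific immunoreaction or off-target editing of CRISPR in the bloodstream". Graft survival and best-corrected visual acuity are separate secondary outcomes. Section 7 and the SAP present the eye examinations descriptively. Neither mentions severity grade.

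**The concern.** HELP is a local treatment of one eye, and the adverse-effect outcome is largely about that eye's structure and function. Three of the four grades ask about something else: whether the person had to stop doing things. Damage found at a visit by slit lamp, pressure measurement, OCT or ERG need not change what the participant does that day, particularly if the other eye sees well. In that situation the grade does not separate a trivial finding from a lasting one.

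The serious-event rules are the natural backstop, but the list that an investigator would apply leaves out the two categories that best fit sight loss or graft failure treated without admission. At stake are the usefulness of a mandatory grade, the immediate notification of sight-threatening events, and the adverse event information that section 10.1 sends to the supervising bodies, in a trial whose secondary objective is safety.

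**Working it through.** The plan states no figure that depends on this scale, so the check is to apply the printed rules to plausible study-eye events.

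**1. Severity under 8.3.**

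| Event in the treated eye | Grade from the printed anchors |
|---|---|
| Graft rejection seen at a visit, activities unchanged | Mild is met; moderate and severe are not |
| The same event, with pain or restriction that makes the participant stop some activities | Moderate, or severe if incapacitating |
| Reduced ERG without symptoms | Mild, if it is recorded as an adverse event at all; 8.1 does not say whether a test finding alone counts |
| Regraft with admission, without extreme limitation of activity | Life-threatening if any one element is enough; otherwise set by the activity anchors alone |

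Rows 1 and 2 may involve the same ocular damage and still receive different grades. Conversely, within row 1 a transient and a permanent injury receive the same grade.

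**2. The top anchor.** It strings together extreme limitation, need for assistance, and "significant medical intervention/therapy required, hospitalization probable". It does not say whether these are joint or alternative conditions, and none of them is a risk of death. In 8.2, life-threatening is an undefined seriousness criterion. The same word is therefore a grade in one section and a seriousness criterion in the next, with no stated link between the two.

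**3. Seriousness under 8.2.** Take graft failure or sight loss in the treated eye, managed without admission:
- Death, hospitalisation and congenital anomaly: not met.
- Life-threatening: not met on any ordinary meaning.
- Persistent or significant disability: depends on the investigator's reading, especially if the eye already saw poorly.
- Permanent damage, or other important medical event: would fit, but these stand only in the opening definition and not in the list.

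The definition would make this event serious; the list may not.

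**4. What else would show the harm.** Graft survival is followed at every visit. Section 3.1 lists acuity, intraocular pressure, anterior-segment photographs, B-scan, OCT and ERG at follow-up, and section 7 and the SAP display the eye examinations. Section 8.3 also requires each event to be recorded and reported in detail. The damage would therefore be on record whatever grade is assigned.

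**5. Scale.** With 3 to 6 participants, moving one participant from one grade to another changes that grade's participant proportion by 1/6 = 16.7 to 1/3 = 33.3 percentage points. This holds for any misclassification in a trial this small. It is not an estimate of error due to this scale.

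**The case against.** The strongest reply is that ocular harm is not hidden. A reader might infer that the trial's safety table will understate damage to the eye. The documents do not support that: no table of events by grade is planned, and graft, vision and ocular examinations are reported in their own right. With so few participants, each eye can be described individually. This stands, and it limits the consequence to the grade and to anything derived from it.

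A reader might also infer that one-eye events can never rise above mild. That is not so. The anchors ask about activities and not about the other eye, and pain, photophobia or restriction can raise the grade. The claim holds only when activities are unchanged. Nor does a regraft necessarily count as life-threatening; that depends on the unstated choice between all and any of the elements.

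The protocol also names an external grading system, whose full content is not in the documents. It may contain eye-specific criteria. But no version is cited, and the four lines that follow are the only rule an investigator can apply from the protocol itself.

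Finally, seriousness is assessed separately from grade, and a death is serious under 8.2 whether or not a fatal grade exists. That is correct, so the missing fatal grade is a matter of completeness. The backstop is still weak where it matters here, because the list omits two categories that its own definition includes.

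**Conclusion.** The point holds in limited form. As printed, the severity grade is uninformative for study-eye events that leave activities unchanged; the top grade is ambiguous and clashes with the use of the same word in 8.2; and the 8.2 list is narrower than its definition. A summary by grade, or a count of serious events based on the list, could mislead. The primary outcome, the separate ocular outcomes and the planned descriptive displays are unaffected.

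The size cannot be put as a number, because the documents give no expected rate of ocular events and no calculation uses the grades. The conclusion assumes that the printed anchors are applied as written and that some study-eye events will leave activities unchanged. The second is plausible for a unilateral treatment, but fellow-eye vision is not described and eligibility requires potential for visual recovery. These are stated rules that can misclassify events at the treatment site, so they should be corrected.

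**What to change.** 1. **Section 8.2:** add permanent damage and other important medical events, naming sight-threatening events and graft failure, to the itemised list so that it matches the definition.
2. **Section 8.3, top grades:** define life-threatening by risk to life, in the same sense as 8.2, and add a fatal grade.
3. **Section 8.3, study eye:** keep the activity scale for systemic events. Add severity anchors for the treated eye based on measures already listed for follow-up: acuity, intraocular pressure, graft status, OCT and ERG. The investigators should set the cut-points and the reference value for change before events are graded. Cite the version of the grading system, and say whether a test finding without symptoms is recorded as an adverse event.
4. **Section 7 and SAP:** list adverse events per participant with eye, grade, seriousness and relatedness. At this sample size a listing is more useful than a table of counts.

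The cost is protocol wording and a grading table on the case report form. No new test is needed, and events already recorded can be regraded from the examinations on file. The downside is that more events will be graded moderate or severe and more will be reported as serious.

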10.1 Ethical Conduct of the Study

The study will be conducted in accordance with the protocol and the requirements according to the concerned laws. The project will be submitted to the supervision parties for censorship. The study will be initiated only with the approval of the IRB & HEC. All the data and information collected from the study will be presented to the supervision parties, especially the information related to AE & SAE. Alteration of the project plan will not be made without the consideration and authorization of the supervision parties. A full report will be provided after the closure of the study.

10.2 Patient Information and Consent

All participants and/or their legal representatives will be fully informed of the objectives and details of this study. All possible outcomes and risks will be acknowledged. A consent of written form will be obtained from each patient or their representatives. The consent process will be witnessed by an

impartial supervisor. A copy of the consent will be provided if requested by the participants. The consent documents will be stored by the investigators along with other data collected during the study for a period required by the protocol. All the personal information and data from the patients will only be available to the investigators and supervision parties to guarantee privacy. The data will not be used for purposes other than this study.

11 Reference

Summary of Protocol Changes

Section of Current protocol	Rationale	Current Version
Basic Information	Adjust the number of participants enrolled	3-6 participants will be enrolled and receive HELP injection during the usual procedure of corneal transplantation.
Outcomes Measures	Adjust the contents and priorities of outcomes	Primary outcome: HSV-1 testing outcome of the intervention eye; Secondary outcome: patient graft survival; best-corrected visual acuity; adverse effects
2.1	Adjust the inclusion criteria	Patients with refractory keratitis caused by herpes virus type I who has acute corneal perforation or had at least one time failed corneal transplant due to the virus relapse.

Original and Current Statistical Analysis Plan

Statistical Analysis Plan

This is an open-label, single-arm, non-randomized interventional trial. The investigators conducted this research to evaluate the safety and efficacy of HSV-1-targeting CRISPR formulation HELP (BD111) for in vivo treatment of refractory HSK patients. In this study, participants will receive a single dose of HELP formulation by intrastromal injection during the penetrating keratoplasty for acute corneal perforation. At each follow-up point, a series of safety and effectiveness evaluations will be performed.

The primary endpoint, HSV-1 in tear swabs will be evaluated at various test points according to the data collection plan, as summarized by simple descriptive summary. For safety evaluations, clinical examinations (slit-lamp examination, measurement of best-corrected visual acuity, intraocular pressure, B-scan ultrasonography, the time-domain OCT, the spectral-domain OCT, and the ERG) will be presented as simple descriptive statistics in the form of pictures, line charts or summarized tables. Deep sequencing of the corneal epithelial cells (acquired by corneal wipes) will also be reported as descriptively summarized tables. Blood ELISA will be reported graphically with the aid of the Student's test. Other laboratory and imaging correlative studies will also be reported descriptively and graphically. Data were analysed using GraphPad Prism 8 and presented as mean \pm SEM in all experiments (n=3). Unpaired two-tailed Student's t-tests were performed to determine the P values (95% confidence interval). n.s., non-significant.

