Shanghai Jiao Tong University, WF220441504

Collaborators: Key Laboratory of Systems Biomedicine,
Shanghai Jiao Tong University

Version 2.0

Version Date: April 12, 2020

Brief Summary:

The purpose of this study is to evaluate the safety, tolerability and efficacy of a single dose of CRISPR/Cas9 mRNA Instantaneous Gene Editing Therapy administered via corneal injection in participants with refractory herpetic viral keratitis.

Condition or disease	Intervention/treatment
Herpes Simplex Virus Infection	Drug: HELP (BD111) Adult single group Dose
Refractory Viral Keratitis	(Administered by corneal injection surgery. Dosage form: injection solution. Dose: 200µL. Frequency of administration: one time injection.)

Description:

This is a single-arm, single dose study of mRNA-carrying HELP (HSV-1-erasing lentiviral particles) in adult (ages 18 to 70) participants with refractory herpetic viral keratitis. 3-6 participants will be enrolled and receive HELP injection during the usual procedure of corneal transplantation. HELP is a novel gene editing formulation designed to clear Herpes simplex virus type I (HSV-1) that results in herpetic stromal keratitis in both acute and recurrent infection models which is the leading factor for infectious blindness. The main outcomes of this study include HSV-1 testing outcome, graft survival, visual acuity and adverse effects of the participants.

Outcomes Measures:

1. Primary Outcome Measure

HSV-1 testing results of the intervention eye. Tear swab of 1 week, 1 month, 2 months, 3 months, 6 months and 12 months post-operation will be collected and quantified for HSV-1 genome by real-time polymerase chain reaction (RT-PCR). The virus testing outcome was indicated as positive (+) or negative (-) by Ct values. Ct value of above 40 will be considered negative, 36-40 be considered weakly positive, and below 35 will be considered a strong positive.

2. Secondary Outcome Measure

- ⑩ Patient graft survival. The corneal grafts of participants will be monitored under a complete ophthalmic examination, including slit-lamp examination and anterior segment optical coherence tomography (OCT), at every follow up visit.
- ⑩ Best-corrected visual acuity. Changes of visual acuity of participants along the clinical trial.

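### With 3-6 participants and a comparator of the same size, the t-test on blood ELISA cannot flag a strong Cas9 response in one or two people, so a non-significant result must not be read as no reaction

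*Combined protocol and SAP*

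**What the plan says.** The secondary outcomes of Version 2.0 include this entry: "Adverse effects, including possible alteration of ocular structure and function, Cas9-specific immunoreaction or off-target editing of CRISPR in the bloodstream". The same entry gives the assays and their timing: "ELISA and Whole-genome sequencing (WGS) will be conducted on the blood samples collected at 3-month and 6-month visit, respectively". It does not say outright that ELISA measures the Cas9 reaction, but no other listed assay plausibly does. Section 3.1 also lists ELISA among the examinations at follow-up visits. No pre-dose ELISA sample is named.

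On analysis, section 7 and the SAP share one sentence: "Blood ELISA will be reported graphically with the aid of the Student's test". The SAP then says that data are presented as mean ± SEM with n=3, and continues: "Unpaired two-tailed Student's t-tests were performed to determine the P values (95% confidence interval). n.s., non-significant". It does not say what the ELISA values are compared with, or whether n=3 counts participants or replicate measurements. No positivity cut-off, per-participant ELISA listing or count of responders appears. The trial is single-arm, and the Description of Version 2.0 sets its size: "3-6 participants will be enrolled and receive HELP injection during the usual procedure of corneal transplantation".

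**The concern.** An immune response to Cas9 happens in individuals: some participants may mount one and others not. A t-test compares group means. When only one or two of a very small group respond, their values raise the standard deviation along with the mean, so the t statistic approaches a ceiling that does not depend on how large the response is. The planned display need not help, because a mean with an SEM bar does not have to show individual points.

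At stake is how one of the few product-specific harms named in the protocol is read. A graph marked n.s. invites the conclusion that no reaction occurred, when a clear laboratory response in one or two people would produce the same mark.

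**Working it through.** The plan states no power, effect size or alpha, so there is no figure of its own to reproduce. The check applies the SAP's test to a simple case.

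**Inputs from the documents**
- Test: unpaired, two-tailed Student's t (SAP).
- Participants: n = 3 to 6 (Version 2.0, Description and Table 1).

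**Assumptions**
- Alpha is 0.05 two-sided, inferred from the SAP's mention of a 95% interval.
- n counts participants.
- The comparator has m values at background. The main case is m = n; larger m is tried below.

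**Limit case.** Let k of n participants rise by x, with everyone else at 0.
- Mean difference = kx/n.
- Pooled variance = x²·k(n−k)/n ÷ (n+m−2).
- With m = n, SE² = x²·k(n−k)/[n²(n−1)], so t = √[k(n−1)/(n−k)] on 2n−2 df.

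x cancels. For k = 1, t = 1 at every n.

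| n | k | t | critical t | p |
|---|---|---|---|---|
| 3 | 1 | 1.00 | 2.776 | 0.374 |
| 3 | 2 | 2.00 | 2.776 | 0.116 |
| 4 | 1 | 1.00 | 2.447 | 0.356 |
| 4 | 2 | 1.73 | 2.447 | 0.134 |
| 5 | 1 | 1.00 | 2.306 | 0.347 |
| 5 | 2 | 1.63 | 2.306 | 0.141 |
| 6 | 1 | 1.00 | 2.228 | 0.341 |
| 6 | 2 | 1.58 | 2.228 | 0.145 |

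Three responders do reach significance: p = 0.024 at n = 4, 0.040 at n = 5 and 0.049 at n = 6. A paired test gives the same t on n−1 df and is no better (one responder p = 0.36 to 0.42, two p = 0.17 to 0.18). One-sided, the smallest p for one or two responders is 0.058.

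**With assay noise.** Share of 40,000 simulated trials with p < 0.05 (noise SD 1, equal groups, unpaired test):

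| Responders | rise 3 SD | rise 10 SD | rise 100 SD |
|---|---|---|---|
| 1 of 3 | 2.8% | 0% | 0% |
| 2 of 3 | 13.7% | 2.2% | 0% |
| 1 of 6 | 4.1% | 0.06% | 0% |
| 2 of 6 | 9.8% | 1.5% | 0% |

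**The display.** With one responder, the variance is x²/n, so SEM = x/n, which equals the mean. The error bar reaches exactly down to background.

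**Larger comparator.** With general m, t = (k/n) ÷ √{[k(n−k)/n ÷ (n+m−2)]·(1/n + 1/m)}. For 1 of 3 against 12 controls: pooled variance = 0.667/13 = 0.0513, SE = √(0.0513 × 0.4167) = 0.146, t = 0.333/0.146 = 2.28 on 13 df, p = 0.040. The smallest m reaching p < 0.05 in the limit case is:
- 1 of 3: m = 12 (p = 0.040)
- 2 of 3: m = 5 (p = 0.034)
- 1 of 6: m = 23 (p = 0.048)
- 2 of 6: m = 11 (p = 0.044)

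**n=3 as replicates.** If three wells are compared with three wells within one participant, a rise of 10 replicate SDs is flagged in essentially every simulated trial, and the cap does not apply. If the wells of three participants are pooled as nine against nine, one responder gives t = 2.00, p = 0.063, and two give t = 4.00, p = 0.001.

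**The case against.** The plan gives the test a modest role. ELISA is to be shown as a graph, and the test only accompanies it. A reader might infer that the presence of an immune reaction is decided by the P value. The documents do not say so: no rule equates n.s. with no reaction, and no safety conclusion or decision is tied to the test. With so few people, individual points might well be drawn, though nothing requires it.

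A reader might also infer that a real immune harm would be reported as absent. That does not follow. Section 8.1 has all adverse events reported whatever their suspected cause. Section 8.3 has them assessed at every follow-up, graded and investigated for their relation to the procedures. Section 4.1 refers separately to noticeable events related to the therapy. This objection stands for clinically evident harm. It does not cover a response seen only in the laboratory: section 8.1 defines an event as an undesirable experience or condition, section 8.3 grades it by effect on activities, and nothing makes a raised ELISA value an event.

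It is also tempting to say that the test fails whatever the comparator, or that a stronger response is always less likely to be flagged. Neither holds. The first needs a comparator of about equal size and n counted in participants, and the SAP settles neither. The second is a large-response result: with 2 of 3 responding, the flag rate first rises from 5% with no shift to about 13% at 3 SD, and only then falls.

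**Conclusion.** The concern holds in a limited form. If n counts participants, the comparator is of equal size and alpha is 0.05, a strong response in one or two of 3-6 participants cannot reach significance: limiting p is 0.34 to 0.37 for one and 0.12 to 0.145 for two. The result disappears with a sufficiently larger comparator or with replicate wells tested within a person. Because the SAP names no comparator and leaves n=3 undefined, it does not exclude the case in which the test is uninformative. What can be masked is a laboratory-only response in one or two participants, not clinically evident harm. The sentence should be changed, because a label of "n.s., non-significant" on this measure cannot support a statement that no Cas9 reaction occurred.

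**What to change.** - In section 7 and the SAP, remove the clause that brings the Student's test into the ELISA report. In the SAP, exempt blood ELISA from the P value and the n.s. label.
- Plot and list each participant's ELISA value at each sampled time, with any available pre-dose value, against an assay positivity cut-off fixed before the samples are read.
- Report the number positive out of the number tested with an exact (Clopper-Pearson) 95% interval. Examples: 1/3, 0.8% to 90.6%; 1/6, 0.4% to 64.1%. With none positive the upper limit is 70.8% for 0/3 and 45.9% for 0/6, so even a clean result would not show absence.
- Where a participant has no pre-dose value, describe a positive as Cas9 reactivity that may pre-date treatment, not automatically as a reaction caused by it.

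The cost is a few sentences and the loss of a P value. A cut-off must be specified in advance; the documents give none, so if the assay does not come with one, setting it may take some laboratory work. No additional participants are needed.

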1.1 Study Objectives

The primary objective of this study is to evaluate the HSV-1 erasing efficiency of HELP with the assistance of corneal transplantation for the treatment of refractory HSK patients. The secondary objective is to determine the safety of CRISPR/Cas9 mRNA Instantaneous Gene Editing Therapy in the form of intracorneal injected HELP. In addition, potential long-term off-target effect of HELP injection should also be determined during the 360 days of follow-ups.

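### The SAP names no interval suited to yes/no results, and its general mean ± SEM (n=3) rule would show zero uncertainty for 0/n or n/n if applied to them

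*Combined protocol and SAP*

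**What the plan says.** **Sample size.** Version 2.0, Description: "3-6 participants will be enrolled and receive HELP injection during the usual procedure of corneal transplantation". The trial has a single arm.

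**Primary outcome.** Version 2.0, Outcomes Measures: "The virus testing outcome was indicated as positive (+) or negative (-) by Ct values". The cut-off is "Ct value of above 40 will be considered negative"; lower Ct values are graded as weak or strong positives. There are six swab visits per participant: "Tear swab of 1 week, 1 month, 2 months, 3 months, 6 months and 12 months post-operation will be collected". Graft survival and adverse effects are among the secondary outcomes.

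**Analysis.** The Statistical Analysis Plan assigns the swabs a purely descriptive treatment, in a sentence that begins "The primary endpoint, HSV-1 in tear swabs will be evaluated at various test points according to the data collection plan, as summarized by simple descriptive". Clinical examinations are also described, in figures or tables. It gives no method for the incidence of adverse events.

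**General rule.** The final lines of the Statistical Analysis Plan present data as mean ± "SEM in all experiments (n=3"). The next sentence reads "Unpaired two-tailed Student's t-tests were performed to determine the P values (95% confidence interval"). No exact or binomial interval appears anywhere in the protocol or the SAP.

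**The concern.** Section 1.1 of Version 2.0 makes viral erasing efficiency the primary objective and adds "The secondary objective is to determine the safety of CRISPR/Cas9 mRNA Instantaneous Gene Editing Therapy". The results the trial hopes for are therefore every swab negative and nobody with a serious event. With 0/1 data those are the results for which the SEM says nothing: identical values have no spread, so the bar has zero width however few people were treated. If the outcomes are simply listed, the reader gets k out of n with no statement of what true rate that excludes. In both cases the plan does not convey how little 3 to 6 participants can rule out, and the error runs towards overconfidence.

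The fixed n=3 adds to this, because it does not match a planned enrolment of 3 to 6. The choice of t-test is a separate matter: correcting the test would not supply an interval for a primary or safety result that has no second group.

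**Working it through.** **Inputs.** n = 3 to 6 and the positive/negative outcome (Version 2.0, Description and Outcomes Measures); six swabs per participant (same place); mean ± SEM with n=3 (Statistical Analysis Plan). The documents give no target rate, power or precision figure, so there is no stated number to reproduce.

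**Step 1. SEM of a unanimous 0/1 result.** SEM = SD/√n. If all values are equal, SD = 0 and SEM = 0 for every n. A t-interval, mean ± t × SEM, then also has zero width.

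**Step 2. What the data allow.** Clopper-Pearson, two-sided 95%: the upper limit for 0/n is 1 − 0.025^(1/n), and the lower limit for n/n is 0.025^(1/n).

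| n | SEM for 0/n or n/n | Upper limit for 0/n | Lower limit for n/n |
|---|---|---|---|
| 3 | 0 | 70.8% | 29.2% |
| 4 | 0 | 60.2% | 39.8% |
| 5 | 0 | 52.2% | 47.8% |
| 6 | 0 | 45.9% | 54.1% |

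**Step 3. How easily no events arise.** P(0 events) = (1 − p)^n. These values of p are assumptions, since the documents give none.
- p = 0.20: 0.8³ = 51.2% at n=3; 0.8⁶ = 26.2% at n=6.
- p = 0.30: 0.7³ = 34.3% at n=3; 0.7⁶ = 11.8% at n=6.

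**Step 4. A mixed result.** For 2/3, SD = √(1/3) = 0.577 and SEM = 0.577/√3 = 0.333, so ±1 SEM runs from 33% to 100%. The exact interval is 9.4% to 99.2%.

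**Step 5. Continuous measures.** For normal data, ±1 SEM covers the mean with probability P(|t| < 1) on n − 1 degrees of freedom: 57.7% at n=3 and 63.7% at n=6. The 95% t-interval is wider by the factor t(0.975): 4.30 with 2 df and 2.57 with 5 df.

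**Step 6. Why the unit must be the participant.** Six visits give 6 × 3 = 18 to 6 × 6 = 36 swabs. Pooling them as independent would put the upper limit for no positives at 1 − 0.025^(1/18) = 18.5% or 1 − 0.025^(1/36) = 9.7%, instead of 70.8% or 45.9%. Repeated swabs from one eye do not carry that much information.

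**The case against.** A reader might infer that SEM is the plan's only stated precision measure and that the plan commits itself to showing 100% ± 0 clearance or 0% ± 0 adverse events. The documents do not support that.

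- The primary endpoint has its own descriptive rule, and a specific rule normally governs over a general closing line. A plain +/− listing carries no error bar, so nothing collapses.
- The SEM sentence follows the laboratory text, speaks of experiments and not participants, is in the past tense and fixes n at 3. It may have been meant for laboratory data.
- A 95% confidence interval is named in the next sentence.
- Zero width needs 0/1 coding. If raw Ct values were averaged, all-negative swabs need not give SEM = 0: assumed values of 40.5, 42 and 44 give 1.01. It would be zero only if undetected samples were set to one constant. The protocol also does not expressly code graft outcome or adverse events as yes/no per participant; adverse events have four severity grades.
- An SEM labelled as such does not claim 95% coverage, and no test or decision rule is attached to swabs or adverse events.

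Most of this stands, and it makes the zero-width bar conditional. It does not remove the gap. The rule is worded to cover all experiments without exception, and the descriptive summary is never defined. The confidence-interval wording belongs to P values from unpaired t-tests, for which swabs and adverse events in one arm have no comparator; an interval built on SEM = 0 would also have no width. On either reading of the general rule, the binary results lack a usable interval.

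**Conclusion.** The point holds as an omission and an ambiguity of scope. The SAP provides no interval suited to its positive/negative primary outcome, to graft failure or to adverse events. Its general display rule would give zero uncertainty for unanimous results if it were applied to them in 0/1 form. It cannot be said that the plan will produce such a display.

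The size of what goes unstated does not depend on which reading is right: at the planned 3 to 6 participants, a result with no events leaves true rates of up to 70.8% to 45.9% open. These limits assume one independent binary result per participant. The 58% to 64% coverage of ±1 SEM assumes normality; it is an argument for better reporting and not an error in the SEM itself. No planned decision turns on these intervals, so this is a cheap and worthwhile improvement to reporting, not a flaw that invalidates the design.

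**What to change.** Replace the mean ± SEM (n=3) sentence in the Statistical Analysis Plan with three rules.

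1. **Binary outcomes.** For HSV-1 negativity at each scheduled visit, and for graft failure, AE and SAE by the end of follow-up, report k/n participants with the exact Clopper-Pearson 95% confidence interval. Count participants (for AE and SAE, those with at least one event), and do not pool the six swabs per participant as independent.
2. **Continuous measures.** Plot each participant's value at each visit. If a mean is shown, give a 95% t-interval.
3. **Denominator.** Set n to the number of participants dosed and evaluated, in place of the fixed 3.

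The cost is a short SAP revision and a few lines of analysis, with no extra participants, visits or samples. The downside is that the reported intervals will be visibly wide.
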